General considerations: All variables will be described and explored using frequency tables, means, medians, standard deviations, histograms, box plots, and trajectory plots, both overall and within clinician. The primary analyses will be conducted on an intention-to-treat basis; clinicians and patients will be analyzed in the group to which they were randomized, regardless of clinician intervention adherence, using all available data. The main conclusions drawn from this trial will be based on the pre-specified hypotheses outlined below and will be tested with two-sided p-values at the standard 0.05 level. For all study outcomes, we will interpret differences between groups over time with reference to prior literature regarding clinically meaningful changes. Results from exploratory analyses will be interpreted with appropriate consideration for their exploratory nature. Statistical analyses will be performed using the latest release SAS for Windows (Cary, NC) and R/Rstudio.

The goal of the primary Hypothesis (1a) is to determine the efficacy of the clinician communication coaching intervention versus usual care on improvement in an objective measure of the quality of communication from baseline to post-training. Additionally, we are interested the intervention effect within Black patients and White patients separately. The quality of communication will be assessed at both baseline encounters and post-training encounters by a summary of clinician-encounter counts derived from the audio recordings. We plan to use mixed-effects models as our primary analytic strategy because they will appropriately account for the intracluster correlation of multiple patient encounters for each clinician and same clinicians followed over time. The mixed-effects model for Hypothesis 1a will have the following form: $\log(\mu_{ijk}) = \mu_0 + \mu_1(post) + \mu_2(post*int_k) + \mu_3(clinrace_k) + b_{0k} + b_{1kj}$, where Y_{ijk} is the number of quality communication statements for patient i at time j clustered within physician i , and Y_{ijk} is assumed to be Poisson with mean and variance equal to μ_{ijk} . The fixed effects in the model include indicator variables for the post-treatment ($post$), intervention group (int), and clinician race ($clinrace$). The random intercepts, b_{0k} and b_{1kj} , are normally distributed and account for dependence of encounters within clinicians, both between patients and on clinicians over time. PROC GLIMMIX (with

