the quadrature option) in SAS (SAS Inc., Cary, NC) will be used to fit the mixed-effects Poisson model and test the primary hypothesis (1a). Specifically, if β_2 is positive and significantly different than zero, this provides evidence of improved communication quality among patients and clinicians in the intervention group as compared to the control group.

The secondary outcome, quality of patient-centered care, is a continuous measure assessed at baseline and post-training. However this is a patient-centered outcome (i.e., the patient's perception) and the same patients are not being followed longitudinally. Therefore, the patients' data collected in the baseline period will not be incorporated in the analysis.

$Y_{ik} = \beta_0 + \beta_1(int) + \beta_3(clinsex_k) + \beta_4(clintype_k) + b_{0k}$, where Y_{ik} is the IPC score for patient i clustered within physician k , and Y_{ik} is assumed to be normally distributed. The fixed effects in the model include indicator variables intervention group (int) and the clinician stratification variables. The random intercept, b_{0k} , is normally distributed and accounts for dependence of patients within clinicians. PROC MIXED in SAS (SAS Inc., Cary, NC) will be used to fit the mixed-effects model and test hypothesis (1b). Specifically, if β_1 is positive and significantly different than zero, this provides evidence of greater IPC among patients of clinicians in the intervention group as compared to the control group.

Hypothesis 1b will be repeated within Black and White patients separately with the goal to ensure that the intervention is effective in each subgroup (as an overall treatment effect can sometimes mask important heterogeneity). Relative differences in the intervention effect on reducing disparities will be addressed in Aim 2.

F.3 Aim 2 Analyses:

Hypothesis 2a: Racial disparities in objective measures of the quality of communication will be lower in encounters with clinicians in the intervention group as compared to encounters with clinicians in the control group.

Hypothesis 2b: Racial disparities in patients' perceptions of the quality of patient-centered care will be lower among those seen by clinicians in the intervention group as compared to encounters with clinicians in the control group.

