A mixed-effects Poisson model will again be the primary modeling strategy for the objective communication outcome Aim 2 analyses. For this Aim, however, the model will include patient-race interaction terms and will have the following form: $\log(\beta_{ijk}) = \beta_0 + \beta_1(Black_i) + \beta_2(T2) + \beta_3(T2*Black_i) + \beta_4(T2*int_k) + \beta_5(T2*Black_i*int_k) + \beta_6(race_k) + b_{0k}$ and b_{1kj} , where Y_{ijk} is the number of quality communication statements for patient i at time j clustered within physician k , and Y_{ijk} is assumed to be Poisson with mean and variance equal to β_{ijk} . Again, the random intercepts, b_{0k} and b_{1kj} , are normally distributed and account for dependence of encounters within clinicians, both between patients and on clinicians over time. In this model, $Black_i$ is the indicator variable for whether a patient is Black (value of 1) or White (value of 0).

Post-treatment, the Black-white mean difference among patients seen by usual care group clinicians is $BWuc = \exp(\beta_0 + \beta_1) - \exp(\beta_0)$, this represents the racial disparity in communication quality. The B-W

mean difference among patients seen by intervention group clinicians is $BW_{int} = \exp(\beta_0 + \beta_1 + \beta_2 + \beta_3) - \exp(\beta_0 + \beta_2)$.

Hypothesis 2a will be tested by β_5 being significantly greater than zero, indicating a greater improvement in the number of quality communication statements for the intervention group versus the control group for Black patients as compared to White patients (i.e., the intervention group reducing the racial disparity). The estimated incident rate ratio, p-value, and 95% confidence intervals will be calculated via estimate statements in PROC GLIMMIX.

A similar linear mixed-effects model (rather than a Poisson) model will be used to examine the reduction in racial disparities of quality of patient-centered care and test Hypothesis 2b. Note that in a linear model framework, the coefficients will represent differences in means rather than rate ratios.

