## Analysis Plan

### F.2 Aim 1 analyses:

*Hypothesis 1a:* As compared to the control group, clinicians randomized to the intervention will have a **greater mean number objective measures of communication quality** in encounters with both Black and White patients combined and in each race subgroup.

The goal of the primary Hypothesis (1a) is to determine the efficacy of the clinician communication coaching intervention versus usual care on an objective measure of the quality of communication from baseline to post-training. Additionally, we are interested the intervention effect within Black patients and White patients separately. The quality of communication will be assessed at both baseline encounters and post-training encounters by a summary of clinician encounter counts derived from the audio recordings. We plan to use mixed-effects models as our primary analytic strategy because they will appropriately account for the intracluster correlation of multiple patient encounters for each clinician. The mixed-effects model for Hypothesis 1a will have the following form:

$\log(\mu_{ik}) = \mu_0 + \mu_1(int) + \mu_2(premean_k) + \mu_3(clinsex_k) + \mu_4(clintype_k) + b_{0k}$ , where  $Y_{ik}$  is the number of quality communication statements for patient  $i$  in the post-period clustered within physician  $k$ , and  $Y_{ik}$  is assumed to be Poisson with mean and variance equal to  $\mu_{ik}$ . The fixed effects in the model include indicator variables intervention group (*int*), each clinician's mean number of quality communication statements per conversation prior to the intervention, and the clinician stratification variables. The random intercept,  $b_{0k}$ , is normally distributed and accounts for dependence of encounters within clinicians. PROC GLIMMIX (with the quadrature option) in SAS (SAS Inc., Cary, NC) will be used to fit the mixed-effects Poisson model and test the primary hypothesis (1a). Specifically, if  $\mu_1$  is positive and significantly different than zero, this provides evidence of greater communication quality among patients and clinicians in the intervention group as compared to the control group.

The analysis for Hypothesis 1a will also be conducted for encounters with white and black patients separately.

*Hypothesis 1b:* Black patients and White patients seen by clinicians in the intervention group will report **higher mean quality of patient-centered care** compared to patients seen by control group clinicians.

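### The protocol and the SAP state different primary models for Hypotheses 1a and 2a, and no visible text says which one governs

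*Protocol*

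**What the plan says.** **Hypothesis 1a, protocol** (Data Analysis & Statistical Considerations). Counts from both periods are outcomes. The fixed effects are post, post*int and clinrace; the indicators listed after post-treatment are "intervention group (int), and clinician race". Two random intercepts, b0k and b1kj, "account for dependence of encounters within clinicians, both between patients and on clinicians over time". The test is on post*int: if it is positive and significant, "this provides evidence of improved communication quality among patients and clinicians in the intervention group as compared to the control group".

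**Hypothesis 1a, SAP** (F.2). The outcome is the count for a patient "in the post-period clustered within physician" k. The fixed effects are int and each clinician's "mean number of quality communication statements per conversation prior to the intervention, and the clinician stratification variables", written premean, clinsex and clintype. There is one random intercept, and the test is on int.

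**Hypothesis 1b.** Both documents give the same post-only model, with clinsex and clintype. The protocol describes its fixed effects as "intervention group (int) and the clinician stratification variables".

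**Hypothesis 2a** (F.3 in each document). In the protocol "the model will include patient-race interaction terms": Black, T2, T2*Black, T2*int, T2*Black*int and clinician race, with two random intercepts, and the test is on T2*Black*int. The SAP uses post-period data with Black, int, Black*int, premean, clinsex and clintype, and one random intercept.

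**Effect of interest.** Protocol F.5 defines it as a pre-post relative difference between arms. The SAP power section defines it as a relative difference in the post-period. The protocol says that the main conclusions rest on pre-specified hypotheses that "will be tested with two-sided p-values at the standard 0.05 level".

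**The concern.** The trial's one primary hypothesis has two written tests that differ in data, tested term, covariates and random effects. If nothing fixes which applies, the model can be chosen after the counts are known, and the stated 5% error rate belongs to neither document alone.

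The protocol also conflicts with itself, whichever document governs. It treats clinician sex and type as stratification variables for 1b, but replaces them with clinician race for 1a and 2a.

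The mismatch reaches the 2a formulas as well: some coefficient labels in each document fit the other document's equation.

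**Working it through.** **1. The two 1a models side by side**

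| | Protocol | SAP |
|---|---|---|
| Outcome data | baseline and post | post only |
| Baseline enters as | outcome | covariate (premean) |
| Tested term | post*int | int |
| Clinician covariates | race | sex, type |
| Random intercepts | clinician, clinician-by-time | clinician |

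The protocol model has no int main effect, so the arms share a baseline mean and exp(post*int) is the post-period rate ratio. Under randomization both models therefore aim at nearly the same quantity. They differ in how they use the baseline data and the covariates.

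**2. Which model the power calculation fits**

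Inputs from the power sections and the SAP table: c = 20 clinicians per arm, m = 6 post encounters each, r0 = 1.0, CV 0.2/0.35/0.5, two-sided 0.05, 80% power. The two-rate formula for cluster trials is

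c = 1 + (1.96 + 0.842)² × [(r0 + r1)/m + CV²(r0² + r1²)] / (r1 − r0)².

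For CV 0.35 and r1 = 1.6: 2.6/6 = 0.433; 0.1225 × 3.56 = 0.436; sum 0.869; divided by 0.36 = 2.415; times 7.849 = 18.96; plus 1 = 19.96, or 20 per arm.

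Solving for r1 gives 1.47/1.60/1.79, against the printed 1.5/1.6/1.8. The plan's figures reproduce from the 240 post-period encounters alone. That is the SAP's comparison; the calculation contains no pre-post term. Both documents print the same 1a figures.

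**3. Both models fitted to the same simulated trials**

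From the documents: 40 clinicians, 4 pre and 6 post encounters each, baseline mean 1.0. Assumed: rho, the share of between-clinician variance common to both periods, is 0.5 or 0.9; covariates are unrelated to outcome except in the last row. Tests are likelihood-ratio tests at 0.05.

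| Setting | rho | SAP power | Protocol power | Verdicts differ |
|---|---|---|---|---|
| IRR 1.6, CV 0.35 (200 trials) | 0.5 | 83.5% | 83.5% | 6.0% |
| IRR 1.6, CV 0.35 (200 trials) | 0.9 | 87.0% | 88.0% | 4.0% |
| IRR 1.5, CV 0.35 (500 trials) | 0.5 | 76.6% | 77.0% | 5-7% |
| IRR 1.5, CV 0.35 (500 trials) | 0.9 | 79.2% | 78.4% | 5-7% |
| IRR 1.6, CV 0.5 (500 trials) | 0.5 | 76.0% | 76.2% | 5-7% |
| IRR 1.6, CV 0.5 (500 trials) | 0.9 | 81.2% | 79.4% | 5-7% |
| Clinician-sex rate ratio 1.5 assumed | not recorded | 82.0% | 77.0% | 7.4% |

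The 5-7% is a range across the four 500-trial rows. In the 200-trial runs the mean estimates are 1.59-1.61 at a true 1.6, and the two models' estimates correlate at about 0.96. With no stratum effect the power gap (SAP minus protocol) runs from −1.0 to +1.8 points. Monte Carlo error is about 1-3 points.

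Under no effect (600 trials, rho 0.5):
- CV 0.2: the tests reject in 4.7% (SAP) and 4.2% (protocol). Verdicts differ in 2.8%, and at least one rejects in 5.8%.
- CV 0.35: the tests reject in 7.2% and 5.3%. Verdicts differ in 3.8%, and at least one rejects in 8.2%.

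Taking whichever test is significant adds about 1 point to the larger single rate (5.8 − 4.7 = 1.1; 8.2 − 7.2 = 1.0).

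**4. Coefficients for 2a**

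This check uses subscripts and the order of terms, since the Greek letters may not have survived text extraction.
- SAP equation: λ3 is Black*int and λ5 is clinsex. The text tests λ5, so read literally it tests clinician sex.
- Protocol equation: β2 is T2, β3 is T2*Black, β4 is T2*int and β5 is T2*Black*int. The printed BWint = exp(β0+β1+β2+β3) − exp(β0+β2) contains no intervention term; it is the post-period gap under usual care. The printed BWuc = exp(β0+β1) − exp(β0) is the baseline gap, not a post-treatment one.
- Both BW formulas fit the SAP's term order, and the SAP's λ5 fits the protocol's β5.

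**The case against.** The strongest reply is that this is a revision carried through unevenly, not a pair of rival tests. The SAP repeats the protocol's paragraphs with changed wording, emphasizes some of the changed phrases, and moves the effect of interest to the post-period. The protocol's 1b model already has the SAP form. Text before the SAP's Analysis Plan heading was not available for this review, so a date or precedence statement may stand there. This carries weight: one can say only that no visible text settles precedence. A reader might infer that the trial deliberately holds two primary tests, and the documents do not support that. A precedence statement would still leave the protocol's covariates inconsistent and the SAP's 2a test mislabelled.

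A reader might also infer that the protocol model is generally weaker. One further set of 600-trial runs did show 74.3% against 69.5% with no stratum effect, and verdicts differing in 7-8%. It records neither the pre-post correlation nor the type I error of either test, and the runs tabulated above do not reproduce the gap. Without a stratum effect, leaving out clinsex and clintype cannot explain a loss. A loss consistent across runs appears only with the assumed clinician-sex rate ratio of 1.5 (82.0% against 77.0%; 80.2% against 74.0% in the further set). The documents give no prognostic effect for clinician sex or type.

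Two more limits stand. The visible randomization text does not mention stratification; that sex and type were the factors is inferred from the 1b model in both documents and the SAP's 1a model. And nothing in the documents makes clinician race an improper covariate in a trial about racial disparities.

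**Conclusion.** The inconsistency is real on the text and concerns the primary test. For both 1a and 2a the documents differ in data, tested term, covariates and random effects, and they define the effect of interest differently. The protocol's 1a and 2a models omit variables that its own 1b model calls stratification variables.

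The practical size is modest. Near the target effect the two 1a verdicts differ in about 4-7% of trials, and choosing the significant one adds about 1 point to the type I error. Power is about equal if clinician sex and type are not prognostic; the protocol model loses about 5-6 points (82.0 − 77.0 = 5.0; 80.2 − 74.0 = 6.2) under the assumed rate ratio of 1.5. These sizes rest on the assumed pre-post share of clinician variance, on likelihood-ratio tests, and, in the 200- and 600-trial runs with recorded settings, on unstratified 1:1 allocation. Hypothesis 2a was checked on its formulas only and was not simulated.

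The reason to act is that the primary test should be fixed before the data are seen. The expected loss of power is not the reason.

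**What to change.** - In both documents, name one governing model for 1a and one for 2a, and date that choice relative to data access. The SAP form is the natural choice: it includes the stratification variables, agrees with 1b, and matches the calculation on 240 post-period encounters.
- State in the protocol whether randomization was stratified, and on which factors.
- Align the effect-of-interest sentences in protocol F.5 and the SAP power section, and the pre-post column labels in the SAP table.
- In SAP F.3, change the tested 2a coefficient from λ5 to λ3.
- If the protocol takes the SAP's 2a equation, its printed BW formulas then fit, but its tested coefficient must change too. If it keeps its own equation, BWuc becomes exp(β0+β1+β2+β3) − exp(β0+β2), and BWint becomes exp(β0+β1+β2+β3+β4+β5) − exp(β0+β2+β4).
- Keep the pre/post model, if wanted, as a labelled sensitivity analysis with clinsex and clintype added. Whether clinician race stays as an extra covariate is the sponsor's choice, to be stated in advance.

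The cost is a wording amendment to both documents. No new data are needed.

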F.4 Missing Data: The survey data may contain missing values in any of the clinician-level and patient-level variables due to drop-out, a missed interim assessment, or item non-response. In addition, there may be a rare instance of audio-recorder mechanical failure or of clinicians or patients turning off the recorder in the middle of the encounter. Our primary analysis technique, hierarchical models, allow for unbalanced or incomplete data and will be fit with maximum-likelihood methods to preserve the missing at random assumption. Additionally, we will thoroughly explore reasons for dropout, and depending upon the type and scope of missing data, variables may be multiply imputed as recommended by Panel on Handling Missing Data in Clinical Trials.²⁸ Note that if needed, we will utilize imputation methods that account for the multiple types of correlation inherent in the clustered data structure.

F.5 Power and Sample Size Considerations: The effect of interest for Aims 1 and 2 pre-post relative difference between the intervention and usual care groups; Aim 1 focuses on the overall difference and the difference within Black and White patients separately, while Aim 2 on the difference within Black patients compared to White patients. The sample size requirements are greatest for Aim 2; as discussed by Leon and Heo (2009), the needed sample size for the patient race-by-intervention group interaction is 4 times that needed for the overall test. For Hypotheses 1a and 2a, our sample size calculations are based upon the difference between two Poisson rates (incident rate ratio) in a cluster randomized design (i.e., patients clustered within clinician). Note that we are not explicitly accounting for the additional clinician-time correlation, so these calculations are conservative. Based on preliminary studies, the baseline mean number of quality communication statements is 1.0, and a conservative range of coefficients of variation (CV) is 0.2 to 0.5 to account for patients clustered within clinician. With a sample size of 240 patients (6 per clinician) and a type-I error of 5%, we will have 80% power to detect incident rate ratios of 1.5 to 1.8 for Hypothesis 1a in the overall test, 1.6 to 1.9 for Black or White patients separately, and 1.8 to 2.1 for Hypothesis 2a.

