For hypotheses 1b and 2b, our sample size calculations are based upon the difference between two means in a cluster randomized design. Again, we are not explicitly accounting for the additional clinician-time correlation, so these calculations are conservative. We present a conservative range of intraclass correlation coefficients (ICC) to account for patients clustered within clinician. With a sample size of 240 patients (6 per clinician) and a type-I error of 5%, we will have 80% power to detect mean differences of effect size 0.37 to 0.44 for Hypothesis 1b in the overall test, 0.52 to 0.56 for Black or White patients separately, and 0.65 to 0.91 for Hypothesis 2b. PASS 15 was used for all calculations.

We plan to enroll approximately 2 clinicians per month and approximately 17 patients per month over 2 years.

Data & Safety Monitoring

The quality of data collection will be enhanced through extensive training of all personnel involved in data collection, with on-going quality assessments conducted while the project is in the field. Quality control checks will include feedback on protocol fidelity, interpersonal skills, and data entry and cleaning. We will also work with an experienced database manager who will oversee the operations, reconcile data from the various sources, conduct data quality assurance, provide reports to the study team, and conduct routine basic data analyses under the supervision of the study statistician. Reconciling differences in data reported from various sources will be on a case-by-case basis, ongoing as data is collected.

Privacy, Data Storage & Confidentiality

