A similar linear mixed-effects model (rather than a Poisson) model will be used to examine the reduction in racial disparities of quality of patient-centered care and test Hypothesis 2b. Note that in a linear model framework, the coefficients will represent differences in means rather than rate ratios.

Power and Sample Size Considerations: The effect of interest for Aims 1 and 2 is the relative difference in the post-period between the intervention and usual care groups; Aim 1 focuses on the overall difference and the difference within Black and White patients separately, while Aim 2 on the difference within Black patients compared to White patients. The sample size requirements are greatest for Aim 2; as discussed by Leon and Heo (2009), the needed

sample size for the patient race-by-intervention group interaction is 4 times that needed for the overall test. For Hypotheses 1a and 2a, our sample size calculations are based upon the difference between two Poisson rates (incident rate ratio) in a cluster randomized design (i.e., patients clustered within clinician).

Based on preliminary studies, the baseline mean number of quality communication statements is 1.0, and a conservative range of coefficients of variation (CV) is 0.2 to 0.5 to account for patients clustered within clinician. With a **sample size of 240 patients in the post period (6 per clinician)** and a type-I error of 5%, we will have 80% power to detect incident rate ratios of 1.5 to 1.8 for Hypothesis 1a in the overall test, 1.6 to 1.9 for Black or White patients separately, and 1.8 to 2.5 for Hypothesis 2a.

For hypotheses 1b and 2b, our sample size calculations are based upon the difference between two means in a cluster randomized design. We present a conservative range of intraclass correlation coefficients (ICC) to account for patients clustered within clinician. With a **sample size of 240 patients (6 per clinician)** and a type-I error of 5%, we will have 80% power to detect mean differences of effect size 0.37 to 0.44 for Hypothesis 1b in the overall test, 0.52 to 0.56 for Black or White patients separately, and 0.65 to 0.91 for Hypothesis 2b. PASS 15 was used for all calculations.

	Number of clinicians	Number of patients in the postintervention phase (number per clinician)	Hypothesis 1a and 2a: Incident Rate Ratio		Hypothesis 1b and 2b: Mean Effect Size	
			CV	Pre-post Relative Rate	ICC	Pre-post Difference

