Aim 1: Overall intervention versus usual care	40 (20 in each treatment arm)	240 (6 per clinician)	0.2 0.35 0.5	1.5 1.6 1.8	0.01 0.05 0.1	0.37 0.41 0.44
Aim 1: Racial subgroup intervention versus usual care	40 (20 in each treatment arm)	120 (3 per clinician)	0.2 0.35 0.5	1.6 1.8 1.9	0.01 0.05 0.1	0.52 0.54 0.56
Aim 2: Racial differences in intervention versus usual care	40 (20 in each treatment arm)	Effective sample size is 60 (1 or 2 per clinician)	0.2 0.35 0.5	1.8-2.2 1.9-2.3 2.1-2.5	0.01 0.05 0.1	0.65-0.91 0.66-0.91 0.67-0.91

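### Protocol F.5 gives 1.8 to 2.1 as the detectable rate ratio for Hypothesis 2a; the SAP gives 1.8 to 2.5 on the same inputs, and 2.1 fits two patients per clinician (80 patients), not the implied 60

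*Protocol*

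**What the plan says.** Protocol F.5 (Power and Sample Size Considerations) bases Hypotheses 1a and 2a on a cluster-randomised comparison of two Poisson rates. The inputs are 240 patients (6 per clinician), 5% type-I error, 80% power, a baseline mean of 1.0 statement and a CV of 0.2 to 0.5. The general considerations say that hypotheses are "tested with two-sided p-values at the standard 0.05 level". For Aim 2 the section states that "the needed sample size for the patient race-by-intervention group interaction is 4 times that needed for the overall test". It then gives the detectable ratio as "and 1.8 to 2.1 for Hypothesis 2a" and, for the patient-reported outcome, the detectable effect size as "and 0.65 to 0.91 for Hypothesis 2b".

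The power section of the SAP repeats the inputs and the factor of 4, but gives "and 1.8 to 2.5 for Hypothesis 2a". The Aim 2 row of its table reads "Effective sample size is 60 (1 or 2 per clinician" and prints "1.8-2.2 1.9-2.3 2.1-2.5" for CV 0.2, 0.35 and 0.5.

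**The concern.** The two documents answer one question differently on the same stated inputs. Only the upper end for 2a differs. The remaining ranges are the same in both: the SAP's "incident rate ratios of 1.5 to 1.8 for Hypothesis 1a in the overall test, 1.6 to 1.9 for Black or White patients separately", the two 1b ranges (0.37 to 0.44 and 0.52 to 0.56) and the 2b range (0.65 to 0.91).

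Both documents say that sample size requirements are greatest for Aim 2, and this line is the Protocol's only power statement for the disparity test on the primary outcome. A Protocol reader would take 2.1 as the worst case at CV 0.5, whereas the SAP's worst case is 2.5. As an excess over 1, that is 1.1 against 1.5. The difference matters most if Hypothesis 2a gives a null result and someone asks what the trial could have detected.

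**Working it through.** **Comparison of the documents, without any formula.** The lower bracket ends in the SAP's Aim 2 row are 1.8, 1.9 and 2.1; the upper ends are 2.2, 2.3 and 2.5. The Protocol's 1.8 and 2.1 are the first and last of the lower ends. The SAP prose runs from the smallest lower end to the largest upper end, 1.8 to 2.5.

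**Inputs for the recalculation.** c = 20 clinicians per arm (SAP table); baseline rate 1.0; CV = 0.2, 0.35, 0.5; two-sided alpha 0.05; power 0.80; m = patients per clinician, so 40m patients in all. The factor of 4 gives 240/4 = 60 patients, or m = 60/40 = 1.5.

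**Formula.** The documents name PASS 15 but not its settings, so the formula is inferred. It is the standard cluster-randomised comparison of two rates, with r the rate ratio:

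c = 1 + (1.96 + 0.8416)^2 × [(1 + r)/m + CV^2 (1 + r^2)] / (r − 1)^2

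Here (1.96 + 0.8416)^2 = 7.849. Solving for r with c = 20:

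| m (patients) | CV 0.2 | CV 0.35 | CV 0.5 | SAP table |
|---|---|---|---|---|
| 6 (240) | 1.47 | 1.60 | 1.79 | 1.5 / 1.6 / 1.8 |
| 3 (120) | 1.65 | 1.77 | 1.95 | 1.6 / 1.8 / 1.9 |
| 2 (80) | 1.81 | 1.92 | 2.09 | 1.8 / 1.9 / 2.1 (lower ends) |
| 1.5 (60) | 1.94 | 2.05 | 2.23 | not given |
| 1 (40) | 2.19 | 2.30 | 2.47 | 2.2 / 2.3 / 2.5 (upper ends) |

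All six Aim 2 values are reproduced after rounding. The Protocol's range is the m = 2 line alone.

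**Limit of the match.** At m = 3 the CV 0.2 and CV 0.5 cells miss on rounding. Without the +1 term that row becomes 1.63/1.74/1.92, which repairs those two cells but misses CV 0.35. That variant also gives 2.42 at m = 1 and CV 0.5, against a printed 2.5, so it fits the Aim 2 row less well. Both variants are carried below.

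**Patients needed for 80% power at the Protocol's endpoints.** Rearranged, m = (1 + r) / [19 (r − 1)^2 / 7.849 − CV^2 (1 + r^2)].

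- r = 1.8, CV 0.2: 2.8 / (1.549 − 0.170) = 2.03, or 81 patients (77 without the +1 term).
- r = 2.1, CV 0.5: 3.1 / (2.929 − 1.353) = 1.97, or 79 patients (72 without).

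All four figures exceed 60.

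**Power at those endpoints with 60 patients.** The standard error is sqrt{[(1 + r)/m + CV^2 (1 + r^2)] / 19}, and power is Φ[(r − 1)/SE − 1.96].

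- m = 1.5 for every clinician: SE 0.327 gives 69% at r = 1.8, and SE 0.424 gives 74% at r = 2.1 (71% and 76% without the +1 term).
- Half the clinicians with 1 patient and half with 2, weighted equally (harmonic mean m = 1.33): 64% and 71% (66% and 73% without). The detectable ratios become 2.01/2.11/2.29.

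**Check of 2b.** A noncentral t calculation with 38 df and design effect 1 + (m − 1) × ICC, at ICC 0.01/0.05/0.1, gives 0.646/0.659/0.674 at m = 2 and 0.909 at m = 1. This matches the printed 0.65 to 0.91, although the method runs up to about 0.02 above the printed 1b rows. The Protocol's 2b range therefore does reach the one-patient end, while its 2a range stops at two.

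**The case against.** The strongest objection is that the shortfall at 60 patients is not peculiar to the Protocol. The lower end, 1.8, also stands in the SAP and would remain after correction, and it too rests on about 80 patients. This is right. What is specific to the Protocol is the missing one-per-clinician end. Changing the number alone would leave a mixed basis undisclosed, so the explanatory clause is needed as well.

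A second objection is that the formula is inferred, that neither document says which bracket end belongs to which cluster size, and that 2.1 also lies inside the printed brackets at CV 0.2 and 0.35. The power percentages should accordingly be read as illustrative. The contradiction itself, and the fact that the Protocol's figures equal the lower bracket ends, need no formula. The cluster-size assignment is an inference, supported by the match of all six cells.

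Third, the SAP redefines the effect as a post-period difference. This does not account for the gap: the Protocol says its calculation leaves the clinician-time correlation out, and every other range carried over unchanged.

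Last, the weight is modest. Hypothesis 1a is the primary hypothesis and its ranges agree, and a reader holding both documents can find the wider range. That keeps this below a critical finding, but the Protocol read alone still misstates its position.

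**Conclusion.** The concern holds. The Protocol's upper detectable ratio for Hypothesis 2a is 2.1 where the SAP has 2.5 on the same inputs. The Protocol's range corresponds to 2 patients per clinician (80 patients), a basis that it does not state and that exceeds the 60 implied by its own factor of 4. Its 2a and 2b ranges also rest on different bases. On the inferred formula the ratio detectable with 60 patients is roughly 1.9 to 2.3, depending on how 1.5 patients per clinician is handled.

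The SAP table discloses its bracket and is not in error. The SAP prose shares one gap with the Protocol: it does not say that the range spans cluster size as well as CV. All of this concerns the plan's surrogate calculation (a two-rate comparison at a reduced sample size), not the power of the race-by-intervention model itself. The correction should be made, but it does not affect the conduct of the trial.

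**What to change.** In Protocol F.5, change the upper figure for Hypothesis 2a from 2.1 to 2.5. In the power text of both documents, add a clause such as: *this range spans 2 to 1 patients per clinician (80 to 40 patients, bracketing the effective sample size of 60) as well as CV 0.2 to 0.5*. The two changes belong together. Leave the SAP table as it is.

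Optionally, add the range for exactly 60 patients (roughly 1.9 to 2.3), but only after confirming it in PASS 15 and stating how 1.5 patients per clinician was handled.

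The cost is one number and one clause in the Protocol and one clause in the SAP. Enrolment, model and test do not change. The only downside is a less favourable stated upper limit in the Protocol.
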